In the event that these more elaborate exposure index calculations are not feasible, two other approaches to the exposure estimate are available. A crude index can be constructed, based solely on the duration of RVN duty and the TCDD concentration of the herbicides used each year. While such an index would be less precise in defining an individual's estimated level of exposure, it would still permit valid comparisons within the RANCH HAND population. Stratification techniques could also be employed using AFSC and duration of exposure (RVN duty) as the grouping criteria.

VI. Statistical Methodology

A. Introduction

The design of the study is presented in schematic form in Figure 6. R' refers to the RANCH HAND personnel and C'' refers to the collection of all possible control individuals. As defined, R' and C'' will contain individuals who are deceased. Since C'' may be 15 to 25 times larger than R', a randomized subsample C' of C'' will be obtained. C' will be constructed from C'' by computer selection of the ten best matched controls for each exposed study subject. As previously noted, close matches will be made for the variables of age, AFSC, RVN tour length, and race. The matched controls will form ten cohorts, C₁ through C₁₀, as previously shown in Figure 1. A 50% random sample from each of the matched control sets of 10 will be selected for inclusion in the mortality assessment so that a group, C' is obtained that consists of 5 matched controls for each exposed subject. These controls will be designated as initial replacement candidates for the morbidity and followup studies. The remaining individuals in the control set will be additional replacement candidates in the event that replacement must occur beyond the members of the mortality set (see Figure 2). C' will be constructed without regard to whether the individual is currently living or dead so that an assessment of mortality can be accomplished.

Referring again to Figure 6, R and C indicate living RANCH HAND members and primary matched controls. If $m_{R'}$ is the proportion of R' found to be deceased, then,

$$R = (1 - m_{R'})R'$$

The questionnaire will provide data concerning specific symptoms and other findings in the R and C groups. Thus, various questionnaire finding rates in R, s_R , will be calculated and compared with the corresponding rates in C, s_C .

[figure not shown]

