Since the death rates r_{1j} and r_{2j} are Poisson variables, they can be contrasted directly. If the relationship of r_{1j} to r_{2j} is found to be consistent between age strata (within statistical variability), a summary mortality index may be calculated. One summary index that will be calculated is Standardized Mortality Ratio (SMR) which is (Armitage, 1971):

$$SMR = M \times 100$$

$$M = \frac{\sum_{j=1}^k m_{1j}}{\sum_{j=1}^k P_{1j} r_{2j}}$$

"Classical" standardized mortality ratios using national mortality data as the reference will not be calculated for RANCH HAND II due to the effects of the healthy worker phenomenon. The term $\sum m_{1j}$ is the total number of deaths observed in the RANCH HAND group while $\sum p_{1j} r_{2j}$ is the number of deaths that would be expected were the age-specific RANCH HAND death rates the same as the age-specific control death rates. Thus the concern is for an SMR greater than 100%. If a crude death rate for controls, d_c , is calculated as

$$d_c = \frac{\sum_{j=1}^k p_{2j} r_{2j}}{\sum_{j=1}^k p_{2j}}$$

then the standardized crude rate for the RANCH HAND group d_{RH} is

$$d_{RH} = M d_c.$$

An approximate statistical test would regard r_{RH} as a Poisson random variable with mean d_c .

An alternative approach to the provision of a proportionate mortality ratio is that of Breslow and Day (1975). In this treatment, a multiplicative model is employed, for example:

$$\lambda_{ijk} = \theta_i \phi_j \psi_k$$

where λ_{ijk} is the mortality rate, θ_i is the contribution due to population differences (RANCH HAND versus Control), ϕ_j is the contribution due to age group, and ψ_k is the contribution due to tour length, etc. The statistical approach here is via maximum likelihood.

Logistic models (Walker and Duncan, 1967) have been extensively studied at USAFSAM for application in cardiovascular disease. These models, in the herbicide context would have the form

$$P = [1 + \exp(\alpha + \beta_1 A + \beta_2 T + \beta_3 R + \beta_4 E + \beta_5 AE + \dots)]^{-1}$$

where

P = probability of death
A = age in years
T = Vietnam tour length
R = indicator variable for race
E = exposure variable

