and where $\alpha_1, \beta_i, i=1,2,\dots$ are coefficients to be estimated from the data. Testing for a group difference can be accomplished by estimating β_4 and interaction coefficients such as β_5 . If all interaction coefficients involving the exposure variable E are zero and E is treated as a 0/1 variable, Cox (1958a, 1958b) has shown that the most powerful test for non-zero β_4 , in the setting of matched pairs, is McNemar's test. This latter test makes full use of the paired design of the study. For McNemar's test, the data are cast into a 2 x 2 table as shown in Table 8. In this table, "a" is the number of pairs in which both members have died, "b" is the number of pairs in which only the RANCH HAND person has died, etc. Using McNemar's test, the test statistic

$$\chi^2 = \frac{|b - c|^2}{b + c}$$

is calculated and referred to the chi-square distribution with one degree of freedom. Cox (1966) and Meittinen (1969) provide extensions of McNemar's test for R controls per exposed (R-to-1 matching). Of course the above analyses will be accomplished considering all deaths, and deaths by specific cause.

TABLE 8
FORMAT OF McNEMAR'S TEST
CONTROLS

RANCH HAND PERSONNEL	DEAD	ALIVE	TOTAL
Dead	a	b	a+b
Alive	c	d	c+d
Total	a+c	b+d	n

As discussed in section V above, RANCH HAND personnel may be characterized as risk takers. This risk taking behavior may be associated with increased mortality from a variety of causes. If herbicide exposure has caused neuropathy in the RANCH HAND personnel, one could anticipate that this disability would increase the probability

of accidental death. Therefore, accidental death rates among RANCH HAND participants will be corrected for risk taking. This can be accomplished by including assessment of risk taking behavior in the questionnaire, indepth interview and psychological evaluation. Both control and RANCH HAND mortality could be corrected using these measures, with the resultant rates being less biased and, therefore, a better indicator of exposed versus control effect.

D. Analysis of Questionnaire and Physical Examination Data

The Questionnaire and Physical Examination will produce data of three types: (1) dichotomous, (2) polytomous and (3) continuous.

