Survival analysis with covariates. These methods allow adjustment of mortality rates or morbidity rates using covariates such as age, race, RVN tour length, AFSC, risk taking score etc. For the purposes of this discussion it will be assumed that the covariables are categorical, that there are only two such covariables and that the covariables do not interact in affecting the hazard of death or morbidity. These assumptions can all be relaxed using available methods.

The hazard function $h_i(t)$ for the i th individual in the study is the function which provides the conditional probability of death or morbid event in the time interval $(t, t+dt)$ given his survival up to time t . The function $H_i(t)$ where

$$H_i(t) = \int_0^t h_i(\tau) d\tau$$

is called the cumulative hazard for the i th individual. It is readily shown that the failure time distribution $F_i^0(t)$ is given by:

$$F_i^0(t) = 1 - \exp(-H_i(t))$$

From this last equation it follows that h_i and F_i^0 are transforms of each other, whence the dependence of F_i^0 on covariables may be modeled via h_i . This may be accomplished as follows. Let $X_i(t)$ and $Y_i(t)$ denote discrete valued stochastic processes pertaining to the i th individual and describing two covariates of interest (e.g., one may be an exposure variable and the other may be covariate such as age or crew position). The basic model for hazard is:

$$h_i(t) = \exp [\xi X_i(t) + \eta Y_i(t)]$$

where ξ and η are "log-relative risks". This model (Frank, 1977) may be extended to allow for any number of possibly interacting factors. Inference about log-relative risks may be drawn using either an approach derived from D. R. Cox (1972) by E. Peritz and R. Ray (1978) or using an approach described by Frank (1977).

F. Statistical Power

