Exposure estimates will be used to sharpen the statistical analysis and can be helpful in summarizing responses. In this discussion, two estimates will be considered: one related to Vietnam herbicide exposure, and another related to domestic (US) herbicide exposure independent of Vietnam experience.

Vietnam herbicide exposure. In the above discussion of statistical methodologies, exposure variables appeared. In the logistic formula on page VI-8, the variable E was shown which could

be either dichotomous, polytomous, or continuous. In the use of logistic functions to discuss study power, the exposure variable was taken as dichotomous. When a polytomous or continuous exposure variable E is constructed, significant sharpening of the study analysis will be accomplished. For example, biases in this study could lead one to suspect that differences between RANCH HAND personnel and controls were in fact due to factors other than a herbicide effect. If however, in addition to differences between RANCH HAND personnel and controls, one was able to show a regression of mortality and/or morbidity on an exposure index E , the case for a bonafide herbicide effect would be firmer. The reconstruction of exposures is discussed in Section V, G.

Domestic herbicide exposure. Individuals in both the RANCH HAND and control groups will have had varying exposure to herbicide in the United States. Particularly, individuals from specific farming and/or foresting areas, may have had and continue to have a significant background exposure. Data on place of residence and information concerning home practices (gardening etc.) could be used to build a background exposure index E_b . In lieu of constructing this index, stratification techniques will be used in the analytic phases of the study.

I. The Replacement Concept

In the mortality analysis, a randomly selected group of control individuals will be compared to the RANCH HAND group, and the data gathered will be analyzed for evidence of herbicide effect. In the questionnaire and physical examination phases of this study, one of the mortality controls will be randomly selected for each RANCH HAND individual. During the physical examination phase, we must anticipate a significant degree of unwillingness to participate, particularly on the part of control personnel. This loss to study can result in significant bias and loss in statistical power; thus the replacement concept has been developed to mitigate these consequences.

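### Section VI.H carries a graded exposure index into a pooled logistic formula with no RANCH HAND term, where a pure group difference can pass for a dose-response

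*Protocol*

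**What the plan says.** Section VI.C (page VI-8) gives a logistic model for the probability of death. Its terms are age, tour length, race, E, an age-by-E interaction and a trailing ellipsis. The key reads "E = exposure variable". The next paragraph explains the group comparison: "Testing for a group difference can be accomplished by estimating" the coefficient of E and its interactions. When "E is treated as a 0/1 variable" and those interactions are zero, the matched-pair test is McNemar's. The model therefore contains both groups, and E carries the contrast between them.

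Section VI.H returns to that formula and says that E could "be either dichotomous, polytomous, or continuous". It adds: "When a polytomous or continuous exposure variable E is constructed, significant sharpening of the study analysis will be accomplished". It raises the possibility that a RANCH HAND excess is due to factors other than herbicide. It answers that if, beyond the group difference, mortality or morbidity also regressed on the index, "the case for a bonafide herbicide effect would be firmer".

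Other sections describe the index differently:

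- The Executive Summary applies regression on the index to exposed men who show symptoms or signs.
- Section V.F(2) describes regression on a normalised index, looking for more signs with more exposure.
- Section V.G(1) calculates an index for each RANCH HAND man and gives none to controls.
- Section V.G(2) says of the crude fallback index that "it would still permit valid comparisons within the RANCH HAND population". It also expects some RANCH HAND men, mainly clerical, to have an index of zero.

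Section VI.E writes a hazard model with two covariates, of which "one may be an exposure variable and the other may be covariate such as age or crew position".

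**The concern.** A regression on dose guards against group bias only if its slope comes from differences among exposed men. In a pooled model with no group indicator and controls at zero, E is partly a label for being RANCH HAND. A step in risk between the two groups then gives a slope on E even when risk is flat among the exposed. The regression would partly restate the group difference and would not be further evidence.

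The protocol itself expects such steps. Table 6 rates combat hazard higher for RANCH HAND than for C-130 crews. Section VIII describes accountability bias, risk-taking behaviour and false positive response. A slope produced by any of these could be read as support for a herbicide effect, in a study whose results are expected to bear on compensation.

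**Working it through.** **No figure to reproduce.** Section VI.H states no power or error rate for the regression on E. The check is of the mechanism.

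**Set-up.** Let G = 1 for RANCH HAND and 0 for controls. Risk is p1 in all RANCH HAND men and p0 in all controls, with no gradient within RANCH HAND. Controls have E = 0. Covariates are left out.

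**Inputs from the protocol:** about 1000 RANCH HAND men (VI.B) and five mortality controls each; 40% examination participation (VIII.G), so about 400 a side; 450 pairs with rates .10 v .05 and .20 v .10 (Table 12); dioxin scale 32/16/2 and three crew classes (V.G); α = .05.

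**Assumptions:** controls at zero; two-sided testing; 10% control rate with bias odds ratios (OR) 1.3 and 1.5 in the 1000 v 5000 and 400 v 400 cases; the share of men at each index level, shown in the table; dioxin score independent of crew score where the two are multiplied.

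**Formula.** With flat risk within each group, corr(E, outcome) = corr(E, G) × corr(G, outcome). The pooled test of E is therefore approximately

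z_E ≈ z_G × corr(E, G), with rejection probability ≈ Φ(z_E − 1.96).

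With q the RANCH HAND fraction, and m1 and m2 the first and second moments of E among RANCH HAND men:

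corr(E, G) = m1·q(1−q) / √{q(1−q)·[q·m2 − (q·m1)²]}.

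**Worked case: mortality, 1000 v 5000, OR 1.3, crew score 1/2/3 held by 33/50/17%.**

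- m1 = .33 + 1.00 + .51 = 1.84; m2 = .33 + 2.00 + 1.53 = 3.86; q = 1/6.
- Variance of E = 3.86/6 − (1.84/6)² = .549; corr = 1.84 × .1389 / √(.1389 × .549) = .925.
- p1 = .1262; difference = .0262; pooled rate = .1044; SE = √[.1044 × .8956 × (1/1000 + 1/5000)] = .01059; z_G = 2.475.
- z_E = 2.475 × .925 = 2.29; Φ(.33) = 63%. Simulation gave 60%.

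**Same calculation, other cases.**

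| Data | Index among RANCH HAND men | corr | z_G | z_E | Closed form | Simulated |
|---|---|---|---|---|---|---|
| 1000 v 5000, OR 1.5 | crew 1/2/3 (33/50/17%) | .925 | 4.00 | 3.70 | 96% | 95% |
| 1000 v 5000, OR 1.3 | dioxin (10/10/80%) × crew | .489 | 2.475 | 1.21 | 23% | 24% |
| 1000 v 5000, OR 1.5 | dioxin × crew | .489 | 4.00 | 1.96 | 50% | 50% |
| 400 v 400, OR 1.5 | crew 1/2/3 (33/50/17%) | .884 | 1.86 | 1.64 | 37% | 36% |
| 400 v 400, OR 1.5 | dioxin × crew | .398 | 1.86 | .74 | 11% | 11% |
| 450 pairs, .10 v .05 | 1/2/3 (30/50/20%) | .887 | 2.85 | 2.53 | 71% | 70% |
| 450 pairs, .20 v .10 | 1/2/3 (30/50/20%) | .887 | 4.20 | 3.73 | 96% | 96% |
| 450 pairs, .10 v .05 | 0/1/2/3 (10/25/45/20%) | .813 | 2.85 | 2.31 | 64% | 64% |
| 450 pairs, .10 v .05 | 32/16/2 (20/20/60%) | .540 | 2.85 | 1.54 | 34% | 32% |
| 450 pairs, .10 v .05 | 32/16/2 (5/10/85%) | .420 | 2.85 | 1.20 | 22% | 22% |

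The 1000 v 5000 and 400 v 400 simulations counted only slopes towards higher risk (nominal 2.5%). The 450-pair simulations counted either direction (nominal 5%). The opposite tail adds less than half a percentage point in any row.

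**With a group term, or RANCH HAND men only.** The rate falls to about 2–4% (nominal 2.5%) in the first set and about 4–6% (nominal 5%) at 450 pairs. With no group difference, the pooled E-only model itself rejects in about 3–5%, so the excess comes from the group step.

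**The case against.** A reader might infer that the protocol has fixed this pooled regression as its main defence against bias. The documents do not support that.

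- Nowhere do controls enter with E = 0, and Section VI.H presents the regression as a step beyond the group contrast.
- Sections V.F(2), V.G(1) and V.G(2), to which VI.H refers for the index, point to a regression within the exposed group, which lacks the flaw.
- The formulas are open-ended. VI-8 ends in an ellipsis and omits the specialty code, a matching variable. VI.E offers its exposure variable as an example and says that the model can be extended.
- If E were entered as separate categories, a flat excess would look flat.
- Section VI.H says only that the case would be firmer. Section VIII.D names the standardised physical examination as the primary correction for questionnaire response bias.
- Exact parameterisation is often left to an analysis plan.

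Most of this stands, and it limits the point to what follows if VI-8 is applied as written. It does not remove it. VI.H ties the graded index to VI-8 by page. The ellipsis cannot hold a RANCH HAND indicator without contradicting VI.C, because E's coefficient would then no longer be the group test. None of the other sections amends the formula. The Executive Summary's alternative selects men on outcome, so it is not a usable substitute.

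**Conclusion.** The point holds conditionally. With a scored or continuous E and controls at zero, VI-8 as written cannot separate a dose-response from a group difference, and its slope is not evidence beyond that difference. The false-positive rate runs from about 11% to over 90%, depending on index shape, sample size and size of bias. Skewed indices on the protocol's 32/16/2 scale give the lower rates; compact three-level scores give the higher ones. The mechanism does not depend on the assumed distributions, but the rates do, because the protocol gives no index distribution. RANCH HAND men with a zero index do not cure it, since the pooled model codes them like controls; 10% of them still left 64%.

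This is an inconsistency between sections that leads to a wrong inference on one literal reading. It should be settled before the index is analysed, but it does not undermine the design or the group comparisons.

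**What to change.** State in Section VI.H that the regression on the index is fitted in one of two ways:

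- among all RANCH HAND men, not only those with symptoms or signs; or
- in the pooled VI-8 model with a RANCH HAND indicator beside the index, as β_G·G + β_E·G·(E − mean E), the mean being taken over RANCH HAND men.

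Say that β_G is the group contrast and that only β_E counts as dose-response evidence. Apply the same rule when a graded exposure variable is used in the Section VI.E hazard model, and bring the Executive Summary into line.

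The cost is one model term and a few sentences in VI.C, VI.E, VI.H and the Executive Summary, with no new data. The dose-response test will have less apparent power because it rests on exposed men only, which is the information actually available on a gradient.

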 - n-butyl 2,4,5-T 60%
 - iso-butyl 2,4,5-T 40%
- (3) Herbicide Green (used from 1962 through 1964)
 - n-butyl 2,4,5-T 100%
- (4) Herbicide Orange (used from early 1965 through 15 April 1970)
 - n-butyl 2,4-D 50%
 - n-butyl 2,4,5-T 50%

Analyses of archived samples of Herbicide Purple suggest that the mean concentration of TCDD may have been approximately 33 ppm (Range: 17 to 47 ppm TCDD) while archived samples of Herbicide Orange may have had a mean concentration of approximately 2 ppm (Range: <0.02 to 15 ppm TCDD).

In addition, two other herbicides were widely used in RVN. These were Herbicide Blue (an organic arsenical formulated from the sodium salt of cacodylic acid), and Herbicide White (a water soluble triisopropanolamine salt formulation of 2,4-D and picloram). The amounts of the various herbicides used in RVN from January 1962 through February 1972 are shown in Table 1.

Table 1. Estimated Quantities of Herbicides and TCDD Sprayed in RVN, Jan 1962-Feb 1972

CHEMICAL	POUNDS
2,4-D	55,940,150
2,4,5-T	44,232,600
TCDD	368
Picloram	3,041,800
Cacodylic Acid	3,548,710
Herbicide Total	106,763,260

Ninety-six percent of the 2,4,5-T disseminated in RVN was contained in Herbicide Orange; the remaining 4 percent in Herbicides Green, Pink, and Purple. However, Herbicides Green, Pink and Purple contained approximately 40 percent of the estimated amount of TCDD disseminated in RVN. Green, Pink and Purple were sprayed as defoliants on less than 90,000 acres from 1962 through 1964, a period when only a small force of U.S. military personnel were in RVN. Ninety percent of all the Herbicide Orange (containing 38.3 million pounds of 2,4,5-T and 203 lb of TCDD) was used in defoliation operations on 2.9 million acres of inland forests and mangrove forests of RVN.

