28 NOV 1979

Most of the herbicide used in RVN was sprayed from aircraft. RANCH HAND aircraft, the C-123, disseminated 88 percent of all herbicide. Helicopters and ground application equipment used by personnel from all branches of the U.S. Armed Forces applied the remaining 12 percent (primarily Herbicide Blue).

Concurrent with the change to Herbicide Orange, the scope of aerial use shifted from four rotating aircrews to 30 permanently assigned aircrews and additional support personnel. Following the announcement in October 1969 that the administration of 2,4,5-T to pregnant rodents caused an increase in the rate of congenital abnormalities, the DOD confined Herbicide Orange spray operations to non-populated areas and in April 1970, all uses of the herbicide were halted. In March 1972, all remaining stocks of 2,4,5-T-containing herbicides were removed from RVN, and transported to Johnston Island, Pacific Ocean, for open storage (Project PACER IVY), and incinerated at sea in 1977 (Project PACER HO). In 1979, the Environmental Protection Agency (EPA) suspended the use of herbicides containing 2,4,5-T because an epidemiologic study in the United States attributed abortogenic effects to its use.

III. Goals of the Investigation

From the above background, three interdependent study goals emerge:

A. Health

(1) To identify veteran and active duty individuals with adverse health effects (physical and psychological) if any, which are attributable to herbicide exposure, and

(2) To identify other individuals at risk of developing future adverse health effects, if such exist.

B. Political

To satisfy the social concern for proper investigation voiced by lay and scientific communities, both national and international.

C. Legal

To clarify the question of compensation awards to the VA claimants.

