²individual not assigned specifically to RH, although may have serviced the aircraft; denominator not ascertainable

³"Morning Reports" may permit ascertainment of this group.

Because of the significant combat hazard associated with low, slow flying missions, all early RANCH HAND crewmembers were elite volunteers (see Risk-Taking Bias, Section VIII). In fact, RANCH HAND crewmembers comprised one of the most highly decorated units during the RVN Conflict. Anecdotal stories reveal that most crew members were, on occasion, heavily exposed to Herbicide Orange due to normal or combat induced equipment malfunctions within the aircraft. Many former RANCH HAND personnel are expected to be currently employed in the aerospace industry as commercial airline pilots, airline managers, and flight mechanics. RANCH HAND personnel still on active duty are expected to be found in senior management positions.

(2) Ancillary Study Groups (Non-RANCH HAND personnel)

Air Force handlers of herbicide drums in RVN were exposed to herbicides because of drum leakage. Advertisements

similar to those proposed for the RANCH HAND personnel may be issued in attempts to define this population. As the drum handlers were ad lib participants, no personnel designator was assigned to these individuals, thus prohibiting computer tracking and identification. The population is unknown, but expected to be small (less than 200) as the majority of drum handlers were known to be Vietnamese. Additional groups such as US Army personnel (officer and enlisted) who flew as observers, US Army helicopter crews, as well as experimental fighter-bomber spray personnel, may be included in the study. Specific epidemiologic/clinical studies for these groups must be planned by a separate protocol following their ascertainment since control group selection will be difficult or moot. It is intended that all data derived from the ancillary study groups will be subsetted for separate analysis and these data will be treated as anecdotal to the primary study.

The members of these groups are expected to be males, ranging in age from 28-68 years. The officer/enlisted ratio is estimated at 1:10. Approximately 10-18% of these populations are expected to be Black. Low numbers of respondents are expected and population at risk ascertainment will not be possible.

(3) Control Group (Not exposed to Herbicide Orange)

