| (2) Crew Chiefs, Aircraft Mechanic, and other Support Personnel: | moderate potential |
| (3) Console Operators and Flight Engineers: | high potential |

The "pilot" group probably received most of their exposure during pre-flight checks as well as during the actual dissemination missions. The crew chief group experienced contact with herbicides during dedrumming and aircraft loading operations as well as during on-site repair of the aircraft and spray equipment. The console operator group was exposed while supervising the loading of the aircraft, during ground testing the equipment, and by tank leakage during dissemination missions.

The available historical records on Operation RANCH HAND indicate that personnel assigned to the project seldom had a "routine" work schedule or environment, thus complicating estimates of the level of herbicide and dioxin exposure. Since actual exposure data (e.g., mg of herbicide/kg body wt) are not available, the establishment of an exposure index will be attempted. The exposure index will be calculated for each RANCH HAND individual to obtain a standardized frequency distribution. The exposure index will be calculated by evaluating the known factors that would have influenced exposure. For aircrew members, these will include such factors as:

- (1) Date of tour with RANCH HAND in Vietnam.
- (2) Number and lengths of tours in Vietnam with RANCH HAND.
- (3) Number of herbicide dissemination missions (as reflected by flying hours and air medals).
- (4) Herbicides employed (yearly records are available that reflect the amount of each herbicide sprayed).
- (5) Crew position.
- (6) Routes of exposure (the major route of exposure for most RANCH HAND personnel was probably percutaneous, although for the console operator, exposure through inhalation may have also been significant).

An exposure index may be derived from consideration of the above factors, i.e., it is a function of those factors:

$$E_I = f(D, T, P, C, R, H),$$

where E_I = Exposure Index

D = Dioxin Concentration Estimate During RANCH HAND Tour

The date of tour with RANCH HAND is important since mean dioxin concentrations in the herbicides changed by a factor of 16 between pre-1965 and post-1965. In 1965, both high and low dioxin formulations were available. Thus, a scale of values for TCDD are:

Pre-196532
196516
Post-19652

T = Duration of Exposure/Number of Missions Flown

P = Proportion of 2,4,5-T Herbicides Used

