The early RANCH HAND aircrew population was an exclusively volunteer group; the C-130 control population, while volunteers in the Air Force, were not volunteers for special hazardous missions. RANCH HAND mission conditions were considered to be more dangerous than those encountered in the normal combat environment. This suggests that some differences may exist in the psychological profiles of the two groups. A sensation seeking or risk taking psychological orientation may have altered the accident mortality or morbidity patterns of the exposed group. In addition, an accident rate affected by peripheral neuropathy could be masked by undetected risk taking behavior bias.

(2) Corrective Measures

In an attempt to correct for the unique psychological factors that affect the choice of an aeronautical career, and to adjust for the effects of combat stress, transport aircrew members were matched with crewmembers of similar transport aircraft. However, the volunteer nature of the early RANCH HAND

operation suggests that this basic matching (as an attempt to control for the psychological effects of combat stress) is not totally ideal. The factors of volunteerism and risk-taking behavior must be considered from both the individual and group perspectives. The assessment of individual risk-taking behavior has been quantified by psychological instruments such as the Sensation Seeking Scale (SSS) of Zuckerman, et al. and the Life Experience Inventory (Torrance). The SSS has been demonstrated to have considerable validity in measuring a variety of phenomena including volunteerism and participation in risky activities and has been applied to naval aviation trainees (Waters). This study was unable to demonstrate an increased accident-related mortality in this group of individuals. These models will be adapted for use throughout all phases of the study.

D. Response Bias

(1) Problem

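### The exposure-index regression offered as support against bias is partly confounded with volunteer selection in the early aircrews, because the index's only fully scaled factor is calendar era

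*Protocol*

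**What the plan says.** Protocol VI.H (Indices and Estimates of Exposure) offers a regression of mortality or morbidity on the index E as support when biases are suspected of producing the group difference. Shown in addition to that difference, it would mean that "the case for a bonafide herbicide effect would be firmer". Section V.F(2) also uses a positive exposure index as part of the context that makes over-reporting a less likely explanation.

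Section V.G(1) defines the index as an unspecified function of six factors: D (dioxin concentration), T (duration or missions), P (share of 2,4,5-T herbicide), C (crew position), R (route) and H (self-reported exposure). D is included because "mean dioxin concentrations in the herbicides changed by a factor of 16 between pre-1965 and post-1965", and is scaled 32, 16 and 2 for before, during and after 1965. C and R have no values yet. If the full index proves infeasible, V.G(2) falls back on a crude index of RVN duration and yearly TCDD concentration, and asserts that it still supports sound comparisons within RANCH HAND.

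On selection, V.B(1)(a) says "all early RANCH HAND crewmembers were elite volunteers", and VIII.C(1) says "The early RANCH HAND aircrew population was an exclusively volunteer group". VIII.C adds that such an orientation may have altered accident mortality or morbidity. II.B states that, with the change to Herbicide Orange, the operation "shifted from four rotating aircrews to 30 permanently assigned aircrews".

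**The concern.** VIII.C treats volunteerism as a difference between RANCH HAND and the C-130 controls. The within-RANCH HAND regression looks free of that problem because everyone in it is RANCH HAND. It is not free of it if the index itself separates an early, volunteer force from a later, larger one. A slope produced by risk-taking, or by anything else that marked early service, could then be read as corroborating a herbicide effect in the very analysis brought in as support against bias. The crude fallback index is the most exposed, since it contains little besides era.

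**Working it through.** **1. The protocol's own figure.** D before versus after 1965: 32/2 = 16, as stated. Section II.B agrees. For Purple, "the mean concentration of TCDD may have been approximately 33 ppm"; Orange had "a mean concentration of approximately 2 ppm"; 33/2 = 16.5. From the shares (40% of the TCDD in 4% of the 2,4,5-T): (0.40/0.04)/(0.60/0.96) = 16.0.

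**2. The P factor.** V.G(1) gives 0.88 for 1962 and 0.66 for 1966. D×P: (32×0.88)/(2×0.66) = 28.16/1.32 = 21.3. On these two years P widens the era contrast.

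**3. Share of aircrew.** V.B(1)(a) gives officer:enlisted ratios of about 2:1 in aircrew and 1:2 overall. If support personnel are all enlisted (the protocol says predominantly), the aircrew share is (1/3)/(2/3) = 50%. Applying 50% to the pre-1965 men is an assumption.

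**4. Era in the index.** Assumptions not in the protocol: multiplicative index; pre-1965 share q of 10-30%; 10% in 1965; other factors independent of era, with combined log SD s of 0.4-1.0. Variance explained by era = V/(V + s²), where V = Var(ln D).

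- q = 10%: mean ln D = 0.1×3.466 + 0.1×2.773 + 0.8×0.693 = 1.178 and V = 0.966. At s = 1.0: 0.966/1.966 = 49%.
- q = 30%: mean = 1.733 and V = 1.658. At s = 0.4: 1.658/1.818 = 91%.

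By simulation, pre-1965 men form 61-98% of the top tenth of the index over the same range. At q = 5% that falls to 37-48%.

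**5. Volunteer status in the index.** Let volunteers be the aircrew half of the pre-1965 men. Variance explained = c²/[v(V + s²)], with c = ½q(3.466 − mean) and v = (q/2)(1 − q/2).

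- q = 10%, s = 1.0: c = 0.1144, v = 0.0475; 0.01308/(0.0475×1.966) = 14%.
- q = 30%, s = 0.4: c = 0.2599, v = 0.1275; 0.06756/(0.1275×1.818) = 29%.

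Their share of the top tenth is half of 61-98%, about 31-49%.

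**6. The crude index.** With an assumed log SD of 0.3 for duration (V.G(1) says most tours lasted one year), era explains 0.966/(0.966 + 0.09) = 91% at q = 10% and 1.658/1.748 = 95% at q = 30%.

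**7. The full index.** Giving C three levels with an assumed one-step ratio of 2 to 5, and q of 5-30%, D accounts for about 33-79% of log-index variance.

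**8. Consequence for a test (illustration only).** Logistic regression of a 10% outcome on log₂(D×T×C), 1,200 men, two-sided 0.05, no herbicide effect, q of 10-30%, volunteer relative risk 1.25-2, one-step C ratio 3:

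| Who is a volunteer | False-positive slope |
|---|---|
| Every pre-1965 man | 9-97% |
| Pre-1965 aircrew only | about 7-48% |
| Pre-1965 aircrew only, perfect volunteer indicator in the model | about 5-8% |

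Simulation error near 5% is about 1 point. The second row is the one that fits the protocol's description.

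**The case against.** The strongest reply has four parts.

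- **Volunteer status is stated for aircrew, not for everyone before 1965.** V.B(1)(a) and Table 5 include the dedicated flight-line maintenance teams of 1962-64. The same section makes aircrew about two-thirds officers, and V.G(1) rates pilots, co-pilots and navigators as low exposure potential, so C partly offsets D for many volunteers. A reader might infer that a high index largely means an early volunteer. Steps 3 and 5 do not support that. The word for early is also never dated. Equating it with pre-1965 is an inference, though the change in force structure in II.B fits it.
- **The index is not fixed.** C and R await separate studies, and V.G(2) gives some men an index of zero, which the log model leaves out. Dominance by era is clear for the crude index, but only likely for the full one.
- **Adjustment is planned.** VI.E lists a risk-taking score and AFSC among the covariates, VI.C corrects accidental deaths for risk taking, and VIII.C adapts sensation-seeking scales for all phases. It would be wrong to say that the plan ignores volunteerism. The gap is narrower: VI.C takes the score from questionnaire, interview and psychological evaluation, so men already dead have none, and accident mortality is an outcome where VIII.C expects the bias. A score also cannot remove other differences tied to early service.
- **The claim in VI.H is modest.** One might read the regression as meant to rule bias out. The text says only that the case gets firmer, in addition to a group difference.

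All four limit the point. None supplies the missing link between era, selection and the index.

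**Conclusion.** The concern holds in a limited form. The era factor is the only one with a full numeric scale, dominates the crude index and probably dominates the full one. Among aircrew it coincides, by inference, with volunteer selection, so the slope on E is partly confounded and the assertion in V.G(2) about the crude index is too strong.

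The size cannot be set from the protocol, which gives no era shares, no volunteer relative risk and no C or R weights. Under the stated assumptions era explains about 49-91% of log-index variance and volunteer status about 14-29%. The first range measures early service and should not be quoted as the extent of volunteer confounding. The false-positive rates show that the effect could range from negligible to serious; they do not estimate it.

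**What to change.** In VI.H and V.G:

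- Report the slope on E within era strata (pre-1965, 1965, post-1965), and separately for aircrew and support personnel, with estimates and confidence intervals beside the overall slope.
- Include the risk-taking score where it is measured, and state that it is unavailable for men who died before assessment.
- Qualify the V.G(2) assertion that the crude index supports sound within-RANCH HAND comparisons.
- State that an overall slope resting only on the between-era contrast is not independent of volunteer selection.

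Two alternatives would not do the job. Using the matched-pair difference as the response leaves the problem in place, because V.B(3)(a) describes all controls as nonvolunteers for high combat risk. Requiring only that the within-era slope share the overall sign is too weak, since that happens about half the time by chance.

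The cost is mainly wording and extra tables. Tour date is already an index input, so era is available for the dead as well as the living. Within-era slopes are less precise and omit the largest dose contrast, which is why the overall slope should stay.
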